13.4.2 Efficacy Analysis

Cecal Intubation Rate

The count and percentage of subjects for which cecum could be reached by the colonoscope with the Pure-Vu will be presented together with 95% confidence intervals.

Proportion of subjects with successful colonoscopy at first attempt

Successful colonoscopy at first attempt is defined as complete procedure conducted as scheduled for the intended indication.

Frequency counts, percentages, and 95% confidence intervals will be provided. In addition, the above proportion will be compared vs. the proportion of subjects that would have underwent a complete procedure at first attempt assuming absence of the Pure-Vu System (as per the data to be captured by the Patient Management Direction). Chi-square or Fisher's exact test, as appropriate, will be performed to evaluate the difference between the two clinical set-ups.

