5.1 Background

Colorectal cancer is the third most common cancer in men and the second most common cancer in women worldwide (2). In the United States, approximately 134,490 new cases are estimated for 2016 with approximately 49,190 deaths (8.0% of all cancer deaths) (3). Because colorectal cancer tends to develop slowly, screening and early detection can significantly reduce both the incidence and associated mortality of the disease (4).

Optical colonoscopy (OC) is considered the gold standard method for the evaluation of subjects with suspected colonic disease. A key factor for ensuring high quality colonoscopy and successful screening is good colon preparation. Bowel preparation prior to colonoscopy is one of the major barriers to patient compliance estimated as many as 38% of patients do not complete the bowel preparation due to palatability and/or intolerance to the large volume. Inadequate preparation is a major obstacle for achieving a high-quality colonoscopy (6).

Inpatient status is one of several factors associated with poor bowel preparation leading to incomplete colonoscopy procedures, which in turn may cause increased patient morbidity, missed pathology, prolonged hospital stay and increased cost. According to results from a

Document Title:	Document No.	Version	Page 12 of 44
Evaluation of the bowel cleansing in hospitalized population using Pure-Vu System	CL00044	4.0	

prospective study by Ness et al. (7) involving a cohort of 649 subjects, inpatient status is a risk factor for bowel preparation failure. Bowel preparation for hospitalized patients can be challenging due to the presence of ongoing acute illnesses, dehydration, comorbidities, and newly prescribed medications. Failure of bowel cleansing typically leads to aborting and re-scheduling procedures after better preparation is achieved, which in turn leads to prolonged hospitalizations.

Pure-Vu System enables colon cleansing during standard colonoscopy using a standard colonoscope with a length of 1630mm – 1710mm and a The Oversleeve, which fits over the colonoscope, is connected to an external workstation, generates fluid jets to break up the feces. The fecal matter & fluids are removed through the evacuation channels of the Oversleeve device into an external waste receptacle.

This study is designed to evaluate the potential improvements in colonoscopy procedure outcomes when using the Pure-Vu System in hospitalized subjects who are indicated for colonoscopy procedure.

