9.2 Secondary endpoints

The following endpoints will be evaluated per study arm:

- Type, incidence, severity, and duration of adverse events.
- Cecum intubation rate
- Proportion of subjects with successful colonoscopy with Pure-Vu for the intended indication in the first attempt.

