12.5 Colonoscopy procedure

Pre-Examination Procedures

- Verify eligibility checked and informed consent was obtained after explaining all risks, benefits, and alternatives to the subject.
- Verify that the study coordinator/nurse has completed the questionnaire regarding the subject's bowel cleansing condition.
- Verify all background/clinical information, demographic and medical history was documented

Document Title: Evaluation of the bowel cleansing in hospitalized population using Pure-Vu System	Document No. CL00044	Version 4.0	Page 26 of 44
---	--------------------------------	-----------------------	---------------

- Verify all connections and assemblies are properly attached (see Instructions for Use)
- Verify device works properly (see Instructions for Use)
- Place and prepare the subject for the colonoscopy procedure.

Colonoscopy Procedures

The insertion during the colonoscopy procedure will be performed by the clinical study investigator(s), experienced in GI endoscopy according to local standard of care. The withdrawal part of the colonoscopy procedure will be performed as per the clinical investigator(s) direction. Physicians in training (residents, fellows) and physician assistants may assist the Study Investigator in any aspect of this part of the procedure as per standard procedures and practices at his/her institution. In cases where upper endoscopy is planned, it will be conducted per the physician's discretion. Anesthesia will be applied as well per the standard of care. In order to ensure correct operation of the Pure-Vu System a Motus GI representative may attend the procedure. Pure-Vu System operation is described in the Instruction for Use.

The colon preparation level for each colorectal segment (ascending, transverse and descending) before the cleansing operation during the insertion phase will be evaluated using the BBPS scoring index (Appendix B).

In case of inadequate bowel preparation defined as BBPS less than 2 in at least one of the colon segments prior Pure-Vu use, the physician will complete a questionnaire as it relates to the subjects management standard of care assuming absence of the Pure-Vu System.

Once the procedure is completed, relevant data will be recorded on the CRF in addition, findings, diagnosis as well as Physician questionnaire will be recorded/completed.

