The colonoscopy examination with the Pure-Vu will be recorded on digital media. Only the subject study ID and initials should appear in the recorded video.

The cecum will be documented in a picture, if applicable.

Document Title:	Document No.	Version	Page 27 of 44
Evaluation of the bowel cleansing in hospitalized population using Pure-Vu System	CL00044	4.0	

All optical colonoscopy still pictures will be saved in a digital format. Quality copies of the pictures taken during optical colonoscopy will be provided to the sponsor and the optical colonoscopy report will be reviewed as part of the monitoring process.

These videos and pictures will be archived and may be used in future analyses to, for example, provide further information about observed lesions or to assess study quality.

Specific situations occurring during colonoscopy

- If the attempt to reach the cecum is failed, the investigator shall perform the procedure with a pediatric or any other colonoscope he/she may choose without Pure-Vu. The subject will complete the study as planned.
- If a medical condition requiring treatment is detected during colonoscopy, the subject will be treated as per the standard care.

Post-Examination Follow-up

Subjects will be transferred to recovery room for observation per clinical site's colonoscopy protocol and will continue his/her medical flow as per the standard of care. Follow-up will be conducted 2 business days (+/- 48 hours) after the procedure to verify that there has been no change in their well-being. Any AE will be documented in the CRF.

Before a subject is considered "lost to follow-up", there must be at least two documented attempts to contact the subject.

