20.0 Appendixes A: Study Design and Schedule of Assessment

	Visit 1	Follow Up
Days	0	2 Business Days (± 48 hours)
Informed Consent	X	
Eligibility assessment (medical records, BMI, etc.)	X	
Medical History, Concomitant Medications, and Demographic details	X	
Assessment of patient's bowel preparation questionnaire	X	
*Assessment of patient's management Directions (filled-in by the physician)	X	
Colonoscopy Procedure	X	
Follow Up	X	X
Adverse Events Reporting	X	X

*for subjects with inadequate bowel cleansing level in at least one segment at baseline.

Document Title:	Document No.	Version	Page 44 of 44
Evaluation of the bowel cleansing in hospitalized population using Pure-Vu System			

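### The with- and without-Pure-Vu first-attempt success rates in Section 13.4.2 use non-equivalent failure rules, so their difference is not cleanly interpretable and the direction of its bias is unknown

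*Combined protocol and SAP*

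**What the plan says.** The endpoint in Section 9.2 is "Proportion of subjects with successful colonoscopy with Pure-Vu for the intended indication in the first attempt"; the synopsis lists it without the words that tie it to the device. Section 13.4.2 defines success: "Successful colonoscopy at first attempt is defined as complete procedure conducted as scheduled for the intended indication". No BBPS threshold or other adequacy condition after cleansing is part of that definition.

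The same section compares this proportion with "the proportion of subjects that would have underwent a complete procedure at first attempt assuming absence of the Pure-Vu System", obtained "as per the data to be captured by the Patient Management Direction", by a chi-square or Fisher's exact test.

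The form behind the comparator is not completed for everyone. Section 12.5 gives its trigger: "In case of inadequate bowel preparation defined as BBPS less than 2 in at least one of the colon segments prior Pure-Vu use". The synopsis and Section 10.0 say the same, and the footnote in Appendix A limits the form to use "for subjects with inadequate bowel cleansing level in at least one segment at baseline".

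Two further rules bear on what counts as success. Under Section 12.5, if the cecum is not reached, "the investigator shall perform the procedure with a pediatric or any other colonoscope he/she may choose without Pure-Vu". Section 13.5 removes withdrawals before the procedure, technical failures and unreached target segments from the primary analysis. Neither section says how such cases count for this secondary endpoint. BBPS is scored before and after Pure-Vu for the primary endpoint (Section 9.1).

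**The concern.** One side of the comparison is something that happened. The other is a physician's judgement about what would have happened, requested only after a low baseline score. Section 5.1 indicates where the sponsor expects that judgement to lead: "Failure of bowel cleansing typically leads to aborting and re-scheduling procedures after better preparation is achieved". No section asks for the matching judgement on the state of the bowel after cleansing.

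This is the only efficacy endpoint with a planned no-Pure-Vu comparison and a test, and it bears on the secondary objective in Section 8.2 about better outcomes for hospitalized subjects. If the two proportions fail subjects for different reasons, part of their difference reflects the counting rules and not the device.

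**Working it through.** **1. Is there a planned figure to reproduce?** No. Section 13.1 gives no sample size reasoning, and no expected rate is stated for this endpoint. The only usable rates are in Section 6.3: adequate cleansing (BBPS ≥ 2 in all three segments) in 25% [17%, 35%] before and 99% [94%, 100%] after Pure-Vu, and cecum intubation in 98%. Assuming n = 97 − 2 = 95, exact (Clopper-Pearson) intervals reproduce the cleansing rates: 24/95 = 25.3% [16.9%, 35.2%] and 94/95 = 98.9% [94.3%, 100.0%].

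**2. The rules side by side.**

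| Situation | With Pure-Vu | Without Pure-Vu |
|---|---|---|
| A segment scores below 2 (after use / at baseline) | Success is still possible if the procedure is called complete | Form is opened; the physician's answer decides |
| All segments adequate, but examination not completed for another reason | Failure can be observed | No form, so no failure can be recorded; success or missing, not stated |
| Cecum not reached, another colonoscope used | Not stated | Not stated |

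The first row can only help the device. The second helps the comparator.

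**3. A simple model of the net effect.** Let
- b = share adequate at baseline: 0.25 (Section 6.3)
- q = share of baseline-inadequate subjects whom the physician says would still have been completed: assumed 0 to 0.5
- f = rate of failure unrelated to cleansing, taken as equal with and without the device: 0.02 (from 98% intubation), with 0.10 as an assumed higher value
- a = share adequate after Pure-Vu among completed procedures: 0.99 (Section 6.3, a rate for all analysed subjects used as a stand-in), with 0.90 as an assumed lower value
- C = b + (1 − b)q = planned comparator rate, counting baseline-adequate subjects as successes

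Planned difference: (1 − f) − C.

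Difference if the device side also required adequacy and the comparator also carried f: (1 − f)a − C(1 − f).

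Bias toward the device = planned − matched = (1 − f)(1 − a) − C·f.

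**4. Numbers.** C = 0.25 at q = 0, and 0.25 + 0.75 × 0.5 = 0.625 at q = 0.5.

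| a | f | q | (1 − f)(1 − a) | C·f | Net, percentage points |
|---|---|---|---|---|---|
| 0.99 | 0.02 | 0 | 0.0098 | 0.0050 | +0.5 |
| 0.99 | 0.02 | 0.5 | 0.0098 | 0.0125 | −0.3 |
| 0.99 | 0.10 | 0.5 | 0.0090 | 0.0625 | −5.4 |
| 0.90 | 0.02 | 0 | 0.0980 | 0.0050 | +9.3 |

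**5. Break-even.** The net effect is zero when 1 − a = C·f/(1 − f): 0.25 × 0.02/0.98 = 0.5%; 0.625 × 0.02/0.98 = 1.3%; 0.625 × 0.10/0.90 = 6.9%. Residual inadequacy above the break-even tilts the comparison toward the device, and below it toward the comparator.

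**6. Sensitivity to two modelling choices.** If the physician were as lenient after cleansing as before, the first term becomes (1 − f)(1 − a)(1 − q). At a = 0.99, f = 0.02, q = 0.5 the net is 0.0049 − 0.0125 = −0.0076, or −0.8 point. If instead none of the device-side failures would have occurred without the device, the offset C·f vanishes and the net is the first term alone: 0.0098, or +1.0 point. The sign remains open.

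**The case against.** The strongest reply is that both sides are worded as a complete procedure, so the written criterion is the same, and that tying success to the indication may imply adequate views. A score below 2 is not automatically a comparator failure either, because the physician decides. This is fair as to wording. But completeness is not defined, and shared words do not make an observed outcome equivalent to a hypothetical answer collected only after a low score.

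A second reply is that the content of the management form is not shown, nor is that of the physician questionnaire completed after the procedure (Section 12.5). This stands. That comparator failures arise only from poor cleansing is inferred from who receives the form. The later questionnaire may ask about repeat examination, but nothing in Section 13.4.2 uses such an answer.

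A reader might infer that the comparison favours the device and that benefit is therefore overstated. The documents do not support that. Limiting the form to baseline-inadequate subjects raises the no-Pure-Vu rate, which works against the device. The inference would be firmer if procedures finished with another colonoscope counted as successes, or if the Section 13.5 exclusions applied here. The plan says neither, and the Section 9.2 wording argues against the first.

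A reader might also expect a bias of several points, for example 0.75 × 0.10 = 7.5 points if one in ten baseline-inadequate subjects stays inadequate. The 75% comes from a study that reduced the preparation so as to produce inadequate colons. The one in ten has no source, and the lower limit of 94% in Section 6.3 corresponds to 6% of all subjects still inadequate after use.

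**Conclusion.** The point holds as one of comparability. As written, the two proportions do not record failure by the same rule, and the plan leaves open how several kinds of case are counted. The missing adequacy condition alone can only favour the device, by about 1 point at the Section 6.3 rates. After the offset, the net is about +0.5 to −0.3 point for q from 0 to 0.5, and its direction in this trial is unknown. These figures assume that Section 6.3 carries over to inpatients on a standard preparation, which is not established, that f is equal on both sides, and that baseline-adequate subjects count as comparator successes. For a secondary endpoint in a feasibility study the likely effect may be small. It should still be corrected, because the comparison carries a test and the remedy is cheap.

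**What to change.** Apply one success rule to both sides in Section 13.4.2, and align Section 9.2 and the synopsis with it.

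- For every subject who triggers the baseline form, have the physician answer the same management question again on the post-use state. Base the comparison on the paired answers, with a paired method such as McNemar's test.
- Add a sensitivity analysis that requires BBPS ≥ 2 in the segments needed for the indication on both sides, using the pre- and post-use scores already collected. Imposing the threshold on the device side only would create a new asymmetry: a subject scoring 1 but judged completable would succeed without the device and fail with it.
- State one rule for counting subjects who are adequate at baseline and so have no form.
- State how switched-colonoscope cases (Section 12.5), technical failures and unreached segments (Section 13.5) count on each side.

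The cost is one repeated CRF item for baseline-inadequate subjects and a few sentences in the plan. The with-Pure-Vu proportion may fall slightly.

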10.0 Study Design

[figure not shown]
This multicenter, prospective, single arm study will include up to 100 subjects (up to 35 subjects per site), aimed at evaluating the performance of the Pure-Vu System in cleansing hospitalized subjects' colon who are indicated for standard colonoscopy procedure. Subjects will be enrolled at up to 6 clinical sites in the United States and Europe

- ❖ Subject consent will be obtained
- ❖ Prior to the colonoscopy procedure, the nurse or study coordinator will be asked to complete a questionnaire including the subjects' bowel preparation type, volume, duration and overall preparation condition.
- ❖ The subject will undergo the colonoscopy procedure with the Pure-Vu system.
- ❖ In case of inadequate bowel preparation defined as BBPS score less than 2 in at least one of the colon segments prior Pure-Vu use, the physician will complete a questionnaire on the patient's management standard of care assuming the absence of Pure-Vu.

Document Title:	Document No.	Version	Page 21 of 44
Evaluation of the bowel cleansing in hospitalized population using Pure-Vu System			

- ❖ Following the colonoscopy with Pure-Vu a follow-up evaluation will be conducted at 48 hours (\pm 48 hours) to assess subject's well-being and capture any adverse events. If the subject is no longer hospitalized, the follow up will be conducted by a telephone call.

Study Flowchart

Document Title:	Document No.	Version	Page 22 of 44
Evaluation of the bowel cleansing in hospitalized population using Pure-Vu System	CL00044	4.0	

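### First-attempt completion with and without Pure-Vu is measured on the same subjects, but section 13.4.2 tests it as two independent groups

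*Combined protocol and SAP*

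**What the plan says.** Section 10.0 describes the design: "This multicenter, prospective, single arm study will include up to 100 subjects". Section 12.2 confirms that there is no randomization and only one arm. Section 9.2 speaks of evaluating endpoints per arm, but no second arm exists.

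Section 13.4.2 defines the observed outcome: "Successful colonoscopy at first attempt is defined as complete procedure conducted as scheduled for the intended indication". It sets this against the proportion that would have had a complete procedure "assuming absence of the Pure-Vu System (as per the data to be captured by the Patient Management Direction"). For the comparison it says: "Chi-square or Fisher's exact test, as appropriate, will be performed to evaluate the difference between the two clinical set-ups". The 95% confidence intervals it mentions accompany the counts and percentages. None is planned for the difference, and no section names a paired method.

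The comparator form is not completed for everyone. Section 12.5 triggers it as follows: "In case of inadequate bowel preparation defined as BBPS less than 2 in at least one of the colon segments prior Pure-Vu use". The footnote in Appendix A agrees: "for subjects with inadequate bowel cleansing level in at least one segment at baseline".

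The success wording varies. Section 9.2 has "Proportion of subjects with successful colonoscopy with Pure-Vu for the intended indication in the first attempt". The synopsis and the definition in 13.4.2 do not require completion with Pure-Vu. Section 12.5 provides that, if the cecum is not reached, "the investigator shall perform the procedure with a pediatric or any other colonoscope he/she may choose without Pure-Vu".

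**The concern.** Each subject supplies an observed result with the device and a judged result without it. Chi-square and Fisher's exact test see only the two totals. They give the same p-value whether the results within subjects agree closely, are unrelated or run in opposite directions. The p-value is therefore not calibrated to the data that the study will produce. The phrase that leaves the choice to what is appropriate selects between two unpaired tests, so it does not let in a paired one.

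This is the only efficacy comparison for which the plan names a test; section 13.3 states a hypothesis for the primary endpoint without one.

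Two smaller gaps affect the same comparison. A subject with BBPS of at least 2 in every segment has no form, and 13.4.2 does not say how that subject enters the comparator. The three statements of success also leave it unclear whether a procedure completed after a change of colonoscope, without Pure-Vu, counts. Both choices influence the size of the reported benefit, so they should be settled before the data are seen.

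**Working it through.** **Inputs.** From the documents: one arm (10.0, 12.2), up to 100 subjects with no statistical basis (13.1), and the unpaired tests (13.4.2). The plan gives no expected rates, power or alpha for this comparison, so there is no planned figure to reproduce. All rates and cell counts below are assumptions, with p-values two-sided and chi-square without continuity correction.

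**Notation.** Cells are (both complete, with only, without only, neither) = (a, b, c, d), with n = a+b+c+d, p1 = (a+b)/n and p2 = (a+c)/n. The difference p1 − p2 = (b − c)/n is the same however the data are analysed.

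**Variance.**
- Unpaired: [p1(1−p1) + p2(1−p2)]/n.
- Paired: the same, minus 2(a/n − p1·p2)/n, which equals [b + c − (b−c)²/n]/n².

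The subtracted term is positive when the two outcomes are positively associated, so the unpaired variance is then too large. Under negative association it is too small.

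**Modest difference: n=100, 93 versus 85, cells (84, 9, 1, 6).**
- Unpaired variance: (0.93×0.07 + 0.85×0.15)/100 = 0.001926, SE 4.39 points.
- Correction: 2×(0.84 − 0.93×0.85)/100 = 0.00099.
- Paired variance: 0.001926 − 0.00099 = 0.000936, SE 3.06 points.
- Asymptotic McNemar: (9−1)²/(9+1) = 6.4, p=0.011.
- Exact McNemar: 2×(1+10)/2¹⁰ = 22/1024, p=0.021.
- Planned tests: chi-square p=0.071, Fisher p=0.112.

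**Same totals, different pairing (93 versus 85).** The planned p-values stay at 0.071 and 0.112 throughout.

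| With only / without only | Association | Asymptotic McNemar | Exact McNemar |
|---|---|---|---|
| 8 / 0 | positive | 0.005 | 0.008 |
| 10 / 2 | positive | 0.021 | 0.039 |
| 12 / 4 | positive | 0.046 | 0.077 |
| 15 / 7 | negative | 0.088 | 0.134 |

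The asymptotic column is below 0.071 in the first three rows and above it in the last, as the variance formula predicts. The exact test is itself conservative: in the 12/4 row it exceeds the chi-square p-value although the association is positive.

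**Larger difference: n=100, 95 versus 81.** Chi-square p=0.002 and Fisher p=0.004. Exact McNemar gives 0.0001, 0.003 or 0.007 with 0, 3 or 5 without-only pairs. Every test rejects.

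**Behaviour with no true difference** (simulation, n=100, 20,000 runs, 80% completing in each condition, nominal 5%). With 5% of subjects in each discordant cell, chi-square rejects 0.1% of the time and exact McNemar 2.3%. With 10% in each, the figures are 1.6% and 3.1%.

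**Denominator.** Let f be the share inadequately prepared and s the share of those who would have been completed anyway; take observed success as 95%.
- All subjects, with the adequately prepared counted as would-have-completed: 0.95 − [(1−f) + f·s].
- Everyone's observed success against form-holders only: 0.95 − s.

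| f | s | All subjects | Mismatched |
|---|---|---|---|
| 25% | 10% | 17.5 points | 85 points |
| 25% | 25% | 13.75 points | 70 points |
| 75% | 10% | 62.5 points | 85 points |
| 75% | 25% | 51.25 points | 70 points |

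The mismatched column is a hypothetical worst case. The 75% figure for f mirrors the 25% adequate at baseline in section 6.3, where subjects were deliberately under-prepared and came from a different population.

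**How plausible is 93 versus 85?** A rate of 85% without the device needs f(1−s) = 0.15, so f is about 17% at s=10% and 20% at s=25%. That is a lower share inadequately prepared than in the denominator table.

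**Success definition.** At n=100, each subject who completes only after a change of colonoscope moves observed success by 1/100 = 1 point. Section 6.3 reports one such subject among 97.

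**The case against.** The strongest reply is that little depends on this. The endpoint is secondary, section 13.1 disclaims any statistical sizing, and if the device works as in section 6.3 the difference will be large enough for any test to reject. That stands, and it limits the severity. It does not make the named test valid for paired data.

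A second reply is that the unpaired test merely errs on the safe side. That is true only under positive association, which is likely here but not assured. A reader might equally infer that a paired test will always give a smaller p-value. It need not: with 95 versus 81 and discordant pairs 17 versus 3, association is positive, yet exact McNemar gives 0.0026 against chi-square 0.0023 (asymptotic McNemar 0.0017). The reason to change is validity, not a better result.

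A third reply concerns the denominator. Section 13.4.2 speaks of a proportion of subjects, and the form is triggered only by inadequate preparation, so the natural reading is that the remaining subjects would have been completed. That is probably the intent. A reader might infer that the plan sets all subjects' success against form-holders only and so inflates the benefit; no section proposes this. What remains is a missing rule. Restricting both proportions to form-holders would be a legitimate subgroup comparison.

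Finally, the comparison with absence of the device suggests that success means success with Pure-Vu, as section 9.2 says. That is reasonable, but the synopsis and 13.4.2 do not say it, and the effect is small.

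**Conclusion.** The test in 13.4.2 is wrong as written: the data are paired and only tests for independent groups are named. This follows from the design and does not depend on any assumed rate. The estimated difference is unaffected; its variance, and hence the p-value, is not right.

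The practical size depends on assumptions. At 93 versus 85 out of 100 with discordant pairs 9 versus 1, the decision at 0.05 changes (0.071 or 0.112 against 0.021 exact, 0.011 asymptotic). At 95 versus 81 it does not. The documents therefore do not support saying that the planned test will create a false positive, hide a real effect or reverse the study's conclusion. Nor is a planned interval at fault, because none is planned for the difference; the fair criticism is its absence.

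The unspecified comparator denominator and the unreconciled success wording are secondary gaps. The point should be fixed, with limited consequence.

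**What to change.** In section 13.4.2, replace the chi-square/Fisher sentence with:

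> Observed completion with Pure-Vu and physician-judged completion without it will be cross-tabulated in one 2x2 table on the same subjects, namely all who undergo the colonoscopy with Pure-Vu, and compared with a McNemar test [exact or mid-p: state one in advance] and a paired 95% confidence interval for the difference. Both discordant counts will be reported. Subjects with BBPS of 2 or more in all segments at baseline count as would-have-completed. A sensitivity analysis limits both proportions to subjects with BBPS below 2 in at least one segment.

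The sensitivity analysis is needed because the main rule assigns a without-device result to adequately prepared subjects, so any observed failure among them becomes a without-only pair by assumption.

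In the synopsis, section 9.2 and section 13.4.2, state in the same words whether completion after a change of colonoscope without Pure-Vu counts as success for this endpoint.

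The cost is a wording amendment with written sponsor and IRB approval (section 15.2). No new subjects are needed. No new assessments are needed either, provided the Patient Management Direction records whether the procedure would have been completed; the form is not reproduced in the documents, so this must be checked. The p-value or the reported difference may become less favourable. The paired test corrects the variance only: the comparator remains a physician's judgement.
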